7.5.1. Clinical Laboratory Evaluations

All laboratory data (hematology and biochemistry), including dipstick urinalysis results will be summarized with descriptive statistics (continuous variables) or as distributions (categorical variables) by visit and treatment group. In addition, the changes from baseline will be summarized as well as the number and percentage of patients with normal or abnormal (i.e., out of reference range) values at each visit for each parameter by treatment group. The out-of-range values will be further classified as clinically significant and clinically not significant based on the investigator's interpretation.

Furthermore, values of selected laboratory parameters will be classified as potentially clinically significant using the following criteria and tabulated in addition to the criteria for abnormality and clinical significance defined above:

- Albumin-L (< 2.5 g/dl)
- Alkaline Phosphatase-H (> 400 U/L)
- Bilirubin, total-H (> 2 mg/dl)
- BUN-H (> 30 mg/dl)
- Calcium-L (< 7 mg/dl)
- Calcium-H (> 12 mg/dl)
- Cholesterol-H (> 300 mg/dl)
- Creatinine-H (> 2 mg/dl)
- GGT-H (> 3XULN)
- Glucose-L (< 50 mg/dl)
- Glucose-H (> 250 mg/dl)
- Phosphorus-L (< 2.0 mg/dl)
- Phosphorus-H (> 5.0 mg/dl)
- Potassium-L (< 3.0 mmol/L)
- Potassium-H (> 5.5 mmol/L)
- SGOT/AST-H (> 3XULN)
- SGPT/ALT-H (> 3XULN)
- Sodium-L (< 130 mmol/L)
- Sodium-H (> 150 mmol/L)

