- 11. Female subjects must be surgically sterile (hysterectomy, bilateral oophorectomy, or tubal ligation), postmenopausal (defined as cessation of menses for at least 1 year), or willing to practice a highly effective method of contraception. All female participants must be non-lactating and non-pregnant and have a negative urine pregnancy test at Screening and at Baseline. Female subjects of childbearing potential must practice a highly effective method of contraception (e.g., oral contraceptives, intrauterine devices, partner with vasectomy), 1 month before enrollment, for the duration of the study, and 3 months after the last dose of study drug. Alternatively, true abstinence is acceptable when it is in line with the subject's preferred and usual lifestyle. If a subject is usually not sexually active but becomes active, the subject and sexual partner must comply with the contraceptive requirements detailed above.
- 12. Willing and able to administer the SC infusion alone or with the assistance of a study partner after a screening period of up to 40 days and willing and able to comply with study requirements.
- 13. Subjects should have a named study partner.

Subjects will be excluded from the study if one or more of the following criteria are applicable:

For Cohort 1 and Cohort 2, the following exclusion criterion applies:

1. Previously unable to tolerate ND0612 and/or have experienced intolerable adverse drug reactions associated with its use, regardless of the dosing regimen administered.

For Cohort 2, the following exclusion criteria apply:

- 1. Atypical or secondary parkinsonism.
- 2. Acute psychosis or hallucinations in past 6 months.
- 3. Any relevant medical, surgical, or psychiatric condition, laboratory value, or concomitant medication which, in the opinion of the Investigator makes the subject unsuitable for study entry or potentially unable to complete all aspects of the study.
- 4. Any malignancy in the 5 years prior to randomization (excluding basal cell carcinoma of the skin or cervical carcinoma in situ that have been successfully treated).
- 5. Positive serum serology for Hepatitis B Virus (HBV), Hepatitis C Virus (HCV) or Human Immunodeficiency Virus (HIV) at the Screening visit.
- 6. Prior neurosurgical procedure for PD, or Duodopa treatment.
- 7. Subjects with a history of drug abuse or alcoholism within the past 12 months.
- 8. Clinically significant ECG rhythm abnormalities.

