8.3.3 Exclusion Criteria

Subjects in **Cohort 1** and **Cohort 2** will be excluded from the study if one or more of the following criteria listed below are applicable.

1. Previously unable to tolerate ND0612 and/or have experienced intolerable adverse drug reactions associated with its use, regardless of the dosing regimen administered.

For **Cohort 2** the following exclusion criteria apply:

- 1. Atypical or secondary parkinsonism.
- 2. Acute psychosis or hallucinations in past 6 months.
- 3. Any relevant medical, surgical, or psychiatric condition, laboratory value, or concomitant medication which, in the opinion of the Investigator makes the subject unsuitable for study entry or potentially unable to complete all aspects of the study.
- 4. Any malignancy in the 5 years prior to randomization (excluding basal cell carcinoma of the skin or cervical carcinoma in situ that have been successfully treated).
- 5. Positive serum serology for Hepatitis B Virus (HBV), Hepatitis C Virus (HCV) or Human Immunodeficiency Virus (HIV) at the Screening visit.

- 6. Prior neurosurgical procedure for PD, or Duodopa treatment
- 7. Subjects with a history of drug abuse or alcoholism within the past 12 months.
- 8. Clinically significant ECG rhythm abnormalities.
- Renal or liver dysfunction that may alter drug metabolism including: serum creatinine >1.3 mg/dL, serum aspartate aminotransferase (AST) or alanine aminotransferase (ALT) >2 x upper limit of normal (ULN), total serum bilirubin >2.5 mg/dL.
- 10. Current participation in a clinical trial with an investigational product or past participation within the last 30 days before Day 1.

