7.5.2. Vital Signs

Vital sign measurements include heart rate (HR), supine and standing blood pressure (BP) (both systolic and diastolic), body temperature, and weight. Furthermore, supine minus standing blood pressure (both systolic and diastolic) will be calculated. The data will be summarized with descriptive statistics by visit and treatment group. In addition, the changes from baseline will be summarized with descriptive statistics.

Furthermore, to identify potentially clinically significant vital signs, the following criteria will be used and tabulated as a shift table by visit:

- Systolic Blood Pressure: <90 mmHg (low), 90-140 mm Hg (normal), >140 mmHg (high)
- Diastolic Blood Pressure: <90 mmHg (low), 90-100 mmHg (normal), >100 mmHg (high)
- Heart Rate: <60 beats per minute (low), 60-100 beats per minute (normal), >100 beats per minute (high).

Orthostatic hypotension will be defined as a reduction in systolic BP of 20 mmHg or more, and/or a reduction in diastolic BP of 10 mmHg or more, for the standing measurement compared to the supine measurement. The proportion of patients with orthostatic hypotension will be tabulated as a shift table by visit and treatment group.

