7.5.3. ECG

The ECGs will be assessed by the investigator and deemed “Normal”, “Abnormal, not clinically significant” and “Abnormal, clinically significant” and tabulated by visit and treatment group.

In addition, the numerical ECG data generated by the central ECG laboratory will be summarized by descriptive statistics for each parameter by visit and treatment group. Also the changes from baseline will be summarized.

The QTc intervals fulfilling the following criteria will be tabulated separately using Fridericia’s correction:

- Values >500 msec
- Values increasing >15% from baseline if baseline value is ≥ 440 msec
- Values increasing >30% from baseline if baseline value is <440 msec

- Values increasing >30 msec from baseline
- Values increasing >60 msec from baseline.

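### The SAP's laboratory flags for potentially clinically significant values take no account of baseline, so the flag table cannot separate new abnormalities from those carried over from entry

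*SAP*

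**What the plan says.** SAP 7.5.1 plans descriptive statistics for the laboratory data by visit and treatment group. It continues: "In addition, the changes from baseline will be summarized as well as the number and percentage of patients with normal or abnormal" (out-of-range) results at each visit, with out-of-range results split by the investigator's view of clinical significance. As a further output, "values of selected laboratory parameters will be classified as potentially clinically significant using the following criteria and tabulated". The list that follows has 19 fixed limits, including "Bilirubin, total-H (> 2 mg/dl". For these flags the section mentions no baseline value, treatment-emergent rule or shift table. It does not say whether the table counts subjects or values, whether it runs by visit, or whether it has a baseline row.

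Protocol 8.3.3 sets numeric laboratory limits at entry in exclusion 9: "serum creatinine >1.3 mg/dL", AST or ALT above twice the upper limit of normal (ULN), and "total serum bilirubin >2.5 mg/dL". These bind one cohort only: "For Cohort 2, the following exclusion criteria apply". The single exclusion shared with Cohort 1 concerns earlier intolerance of ND0612.

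Other safety sections of the SAP do use baseline. In 7.5.2 the vital sign limits are handled so that "the following criteria will be used and tabulated as a shift table by visit", and orthostatic hypotension also gets a shift table. In 7.5.3, four of the five QTc criteria are relative to baseline, for example "Values increasing >30% from baseline if baseline value is <440 msec". In 7.3.4 only events that begin or worsen from the first dose onward are summarised.

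**The concern.** A flag on the value alone cannot distinguish a subject who crossed the limit after starting ND0612 from one who was beyond it before the first dose. Bilirubin makes this concrete, because the protocol admits values that the SAP then flags.

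Laboratory data are a secondary safety measure in an open-label study with no untreated control. There is no comparison group in which pre-existing abnormality would show up and could be discounted, so each subject's own baseline is the only reference. A flag table that ignores it may be read as showing more new laboratory abnormality on ND0612 than occurred. For flags that are rarely met, a few carried-over subjects could form a noticeable part of the count.

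**Working it through.** No sample size, power or error-rate figure is involved, so there is no stated figure to reproduce. The check compares entry limits with flags, classifies a stable subject, asks what the other planned tables can recover, and sizes the effect under a stated assumption.

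**1. Entry limit against flag** (Protocol 8.3.3, exclusion 9; SAP 7.5.1)

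| Parameter | Excluded if above | Flagged if above | Entry limit minus flag |
|---|---|---|---|
| Total bilirubin, mg/dL | 2.5 | 2.0 | 2.5 − 2.0 = +0.5 (overlap) |
| Creatinine, mg/dL | 1.3 | 2.0 | 1.3 − 2.0 = −0.7 (none) |
| AST and ALT, × ULN | 2 | 3 | 2 − 3 = −1 (none) |

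Bilirubin is the only parameter with a numeric entry limit whose flag lies inside the range allowed at entry. The overlap is values above 2.0 and up to 2.5 mg/dL.

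**2. The rest of the list.** Of the 19 flags, 3 (creatinine, AST, ALT) have an entry limit stricter than the flag and 1 (bilirubin) has a looser one. The remaining 19 − 3 − 1 = 15 have no numeric entry limit in this protocol.

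**3. A stable subject.** Take a hypothetical Cohort 2 subject with baseline bilirubin 2.3 mg/dL and later values 2.1, 2.3 and 2.5.
- Rule as written (value > 2): 3 of 3 post-baseline values are flagged.
- Same rule, also requiring baseline ≤ 2: 0 of 3 are flagged as new.

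**4. What the other planned tables recover.** Suppose two subjects meet a flag at baseline and two meet it at Month 6. If *k* of them are the same people, the number newly flagged is 2 − *k*, that is 2, 1 or 0 for *k* = 0, 1 or 2. Counts by visit are identical in all three cases. Group summaries of change from baseline do not settle it either, because they do not cross a subject's baseline flag status with later status.

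**5. Size.** The documents give no prevalence. As an assumption only, let 0.5% to 3% of subjects enter with bilirubin in the overlap. Expected number = N × p, and chance of at least one = 1 − (1 − p)^N.

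| N (source) | p = 0.5% | p = 3% |
|---|---|---|
| 120 (SAP 3.3, lower) | 0.6 | 3.6 |
| 170 (SAP 3.3, upper) | 0.85 | 5.1 |
| 210 (Protocol 11.2) | 1.05 | 6.3 |

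The chance of at least one such subject runs from 0.452 (N = 120, p = 0.5%) to 0.998 (N = 210, p = 3%). These use the whole-study N, although the 2.5 mg/dL limit applies only to Cohort 2.

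**The case against.** **The SAP does not call the flags on-treatment findings.** A reader might infer that it deliberately counts entry abnormalities as effects of ND0612. The text does not support that: the layout is left open, and a table by visit could show baseline alongside later visits, since safety laboratory tests are taken on Day 1. This stands. A baseline row would still not link the same subject across visits, as step 4 shows.

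**New shifts can be found elsewhere.** It would go too far to say that a new shift cannot be told from a carried-over value. Changes from baseline are summarised, all data are listed by patient, and an abnormal laboratory finding can be reported as an adverse event, which is summarised only if treatment-emergent. The gap is confined to the planned flag tables.

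**The two bilirubin limits do not contradict each other.** An entry limit and a reporting flag serve different purposes. This stands, and the point does not ask for either to change.

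**The flags are not an isolated case.** The Epworth cut-offs (10 and 18), the VAS pain cut-offs (above 0 and at least 40 mm) and QTc above 500 msec also have no baseline condition. That is correct. It weakens any charge of singular inconsistency but does not make the laboratory table more informative.

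**Counts of flags that could be positive at entry are easily overstated.** From the numeric limits alone, one might infer 16 of 19 for Cohort 2 and 19 of 19 for Cohort 1. For Cohort 2, inclusion 10 and exclusion 3 let the investigator keep out subjects with laboratory abnormalities, and exclusion 9 is not worded as exhaustive. Cohort 1 entered through ND0612H-006, whose eligibility criteria are not in these documents. Its general baseline also precedes dosing in that study, so an abnormality at entry to the present study could be a drug effect. Neither count should be relied on.

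**Conclusion.** The point holds as a weakness in one descriptive table. None of the 19 laboratory flags is conditioned on baseline, and for bilirubin the protocol allows entry values that already meet the flag. An unchanged value is therefore classified exactly like a new one, and no planned table crosses baseline flag status with later status.

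The size is limited. The primary measures (adverse events, pain VAS and tolerability) are untouched and no hypothesis test is involved. The number of subjects affected is unknown and probably small. The illustrative range of about 0.6 to 6.3 subjects for bilirubin rests entirely on an assumed prevalence of 0.5% to 3%. The documents do not support a claim that carried-over values would make up most of any count. The change is still worth making, because without an untreated control the within-subject comparison is what gives this table its meaning, and the data are already collected.

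**What to change.** In SAP 7.5.1, leave all thresholds as they are and change the tabulation:

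- Present each criterion as a baseline by post-baseline shift table, as 7.5.2 does for vital signs.
- Report the number and percentage of subjects newly meeting it after baseline, with subjects not meeting it at baseline as the denominator.
- Show separately the subjects already meeting it at baseline.
- State that baseline is the SAP 5.2 baseline, which for Cohort 1 is the last value before first dosing in ND0612H-006. Abnormalities that arose during that earlier exposure are then not set aside as pre-existing.

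The cost is a few lines of SAP text and one extra table shell, with no new data. The denominators for newly flagged subjects become slightly smaller.

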7.5.2. Vital Signs

Vital sign measurements include heart rate (HR), supine and standing blood pressure (BP) (both systolic and diastolic), body temperature, and weight. Furthermore, supine minus standing blood pressure (both systolic and diastolic) will be calculated. The data will be summarized with descriptive statistics by visit and treatment group. In addition, the changes from baseline will be summarized with descriptive statistics.

Furthermore, to identify potentially clinically significant vital signs, the following criteria will be used and tabulated as a shift table by visit:

- Systolic Blood Pressure: <90 mmHg (low), 90-140 mm Hg (normal), >140 mmHg (high)
- Diastolic Blood Pressure: <90 mmHg (low), 90-100 mmHg (normal), >100 mmHg (high)
- Heart Rate: <60 beats per minute (low), 60-100 beats per minute (normal), >100 beats per minute (high).

Orthostatic hypotension will be defined as a reduction in systolic BP of 20 mmHg or more, and/or a reduction in diastolic BP of 10 mmHg or more, for the standing measurement compared to the supine measurement. The proportion of patients with orthostatic hypotension will be tabulated as a shift table by visit and treatment group.

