11.1.3.2 Secondary Safety Measures

The secondary safety endpoints to be assessed for the 12-month treatment period include:

- Assessment of suicidal behavior and ideation (C-SSRS responses, including the number of subjects experiencing at least 1 event of suicidal ideation, at least 1 event of suicidal behavior, at least 1 event of suicidal ideation or behavior and self-injurious behavior without suicidal intent, changes from Baseline in C-SSRS categories (No Suicidal Ideation or Behavior, Suicidal Ideation and Suicidal Behavior) and changes from Baseline in C-SSRS suicidal ideation)
- Assessment of impulsive compulsive behavior (QUIP-RS total scores)
- Epworth Sleepiness Scale (ESS total score)
- Vital signs with a focus on orthostatic BP (possible dopaminergic side effect)
- Laboratory data (hematology and biochemistry), including dipstick urinalysis results evaluation
- 12-lead ECG parameters, including ECG interpretation of clinical significance
- Physical examination
- Prior and concomitant medications

The definition of the other safety endpoints and the corresponding analyses will be detailed in the SAP.

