3.2.2. Secondary Safety Measures

The additional secondary safety outcome measures include:

- Suicidality (C-SSRS)
- Questionnaire for Impulsive-Compulsive Disorder (QUIP-RS)
- Excessive daytime sleepiness (ESS)
- Vital signs, including evaluation of orthostatic hypotension
- Laboratory tests

- ECG data.

The definitions and analyses of these safety measures are provided in Section 7.5 of this SAP.

8.3

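### SAP 7.5.2 gives diastolic pressure the systolic lower limit of 90 mmHg, so the diastolic shift table labels ordinary values low and shows no shift for any fall from below 90

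*SAP*

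**What the plan says.** SAP 7.5.2 introduces a set of categories "to identify potentially clinically significant vital signs, the following criteria will be used and tabulated as a shift table by visit". There are two blood pressure lines:

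- The first line, for systolic pressure, reads "Systolic Blood Pressure: <90 mmHg (low), 90-140 mm Hg (normal), >140 mmHg (high".
- The second line, which is the one at issue here, reads "Diastolic Blood Pressure: <90 mmHg (low), 90-100 mmHg (normal), >100 mmHg (high".

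The same section plans other outputs that do not use these bands. Blood pressure and the supine-minus-standing difference are summarised by visit, and "In addition, the changes from baseline will be summarized with descriptive statistics". Orthostatic hypotension has its own rule and its own shift table: "Orthostatic hypotension will be defined as a reduction in systolic BP of 20 mmHg or more, and/or a reduction in diastolic BP of 10 mmHg" as a minimum, judged on the standing reading against the supine one.

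Vital signs are a secondary safety measure. SAP 3.2.2 lists "Vital signs, including evaluation of orthostatic hypotension", and Protocol 11.1.3.2 lists "Vital signs with a focus on orthostatic BP (possible dopaminergic side effect". Protocol 11.1.3.2 and 11.1.4.2 leave the detailed safety definitions to the SAP, and the SAP Preface says that the SAP prevails over the protocol's statistical sections. The diastolic line in SAP 7.5.2 is therefore the operative definition.

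**The concern.** The diastolic lower limit repeats the systolic one. It may have been carried over from the line above, although the documents cannot confirm that. A diastolic reading must reach 90 mmHg to count as normal, and the normal band then ends at 100.

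The table is meant to pick out values of possible clinical significance and to show movement from baseline. With the lower limit at 90, most plausible readings sit in the lowest band at baseline. That has three effects:

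- ordinary values are flagged;
- a subject who starts below 90 can fall any distance without a recorded shift;
- a rise from 75 to 95 mmHg appears as a move from low to normal, which reads as an improvement.

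Blood pressure lowering is the effect that the protocol singles out among vital signs as a possible dopaminergic side effect. A diastolic table that cannot show it fails at its purpose.

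**Working it through.** The plan has no sample size, power or derived figure to reproduce here. The check applies the SAP's bands as written.

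**Inputs, all from SAP 7.5.2.** Systolic: low below 90, normal 90 to 140, high above 140 mmHg. Diastolic: low below 90, normal 90 to 100, high above 100 mmHg.

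**1. The two lines together.** Diastolic pressure is below systolic pressure. A subject at systolic 90 is normal on the systolic line and must be low on the diastolic line. For both readings to be normal, diastolic must be at least 90, so pulse pressure can be at most systolic minus 90:

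| Systolic (mmHg) | Largest pulse pressure with both normal (mmHg) |
|---|---|
| 90 | 90 − 90 = 0 (not possible) |
| 100 | 100 − 90 = 10 |
| 110 | 110 − 90 = 20 |
| 120 | 120 − 90 = 30 |
| 130 | 130 − 90 = 40 |
| 140 | 140 − 90 = 50 |

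The normal band is 140 − 90 = 50 mmHg wide for systolic and 100 − 90 = 10 mmHg wide for diastolic.

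**2. What the shift table records.** This step needs no outside figure.

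- All whole-mmHg falls from baselines of 40 to 89, down to 20, were enumerated. None of the 2,225 changes category.
- A 10 mmHg fall changes category only from baselines of 90 to 99 (normal to low) or 101 to 110 (high to normal). It never does so from a baseline below 90. For comparison, 10 mmHg is the diastolic drop on standing that the same section treats as orthostatic hypotension.
- 89 to 55 is low to low; 91 to 89 is normal to low; 95 to 80 is normal to low; 75 to 95 is low to normal.

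**3. How many readings are affected.** The documents give no diastolic distribution. **Assumption:** normal, mean μ of 70 to 85 mmHg and SD σ of 8 to 12 mmHg. With Φ the standard normal distribution function:

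- low = Φ((90 − μ)/σ)
- normal = Φ((100 − μ)/σ) − Φ((90 − μ)/σ)
- high = 1 − Φ((100 − μ)/σ)
- recorded as moving to low if every subject falls by 15 mmHg = P(90 ≤ baseline < 105) = Φ((105 − μ)/σ) − Φ((90 − μ)/σ)

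| Mean, SD | Low | Normal | High | Recorded move to low after a 15 mmHg fall |
|---|---|---|---|---|
| 70, 8 | 99.4% | 0.6% | 0.0% | 0.6% |
| 75, 10 | 93.3% | 6.1% | 0.6% | 6.5% |
| 80, 10 | 84.1% | 13.6% | 2.3% | 15.2% |
| 85, 10 | 69.1% | 24.2% | 6.7% | 28.6% |
| 85, 12 | 66.2% | 23.3% | 10.6% | 29.1% |

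Worked case, mean 75 and SD 10: low = Φ(1.5) = 0.933; low or normal = Φ(2.5) = 0.994; normal = 0.994 − 0.933 = 0.061.

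Over the whole grid, low runs from 66% to 99%, normal from 1% to 24% and high from 0% to 11%. Treating readings as rounded to whole mmHg gives nearly the same picture: 65% to 99% low and 1% to 27% normal.

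**The case against.** The strongest case on the other side is about weight. Vital signs are secondary, nothing is tested on this table, and no primary result uses it. A diastolic fall remains visible in the by-visit statistics, the changes from baseline, the orthostatic table and the listings. This stands, and it limits the reach of the point. It does not replace the table. The continuous summaries describe groups, the orthostatic rule compares standing with supine rather than with baseline, and listings do not tabulate. Nothing else in SAP 7.5.2 classifies an individual subject's diastolic level.

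Any banded table also hides falls within its lowest band. The systolic row (below 90) and the heart rate row (below 60) do so too. That is true in kind. The difference is where the limit sits: here the lowest band holds most plausible readings rather than the extreme ones.

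The SAP applies the bands to each measure separately and does not require both to be normal at once. A systolic normal with a diastolic low is therefore not a logical contradiction, and at systolic 130 or 140 the permitted pulse pressure of 40 or 50 mmHg is less restrictive. This stands. The pulse pressure table shows that the limits fit poorly together; it does not prove an error by itself.

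Finally, the percentages rest on an assumed distribution. They do, but most readings are low at every value tried, and step 2 needs no assumption.

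**Conclusion.** The diastolic line is wrong as written for its stated purpose. From the SAP's rule alone, no fall from a baseline below 90 mmHg can appear as a shift. Under the assumed distributions (mean 70 to 85, SD 8 to 12 mmHg), about two thirds to nearly all readings are classed low, and a uniform 15 mmHg fall is recorded as a move to low in at most 29% of subjects. The 15 mmHg fall is an illustration, not a forecast. That readings classed low are ordinary values rests on general knowledge of diastolic pressure, since the documents do not define an ordinary value.

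The effect is limited to the diastolic rows of this secondary table. It should be corrected, but it does not threaten the primary safety conclusions.

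**What to change.** Before the table is produced, the sponsor should replace the diastolic lower limit in SAP 7.5.2 with a diastolic-specific value that it chooses and documents. The normal band should then run from that value to the existing upper limit of 100 mmHg, which the sponsor can confirm at the same time. If 90 is intended, the SAP should say why. No replacement value is proposed here, because the documents give none.

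The SAP Preface allows updates until final database lock. Settling the limit before results are seen avoids a post-hoc choice. The cost is one line in the SAP and one programming format. No data collection and no other analysis changes.
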